8.2. DISCUSSION OF TRIAL DESIGN

As a post-marketing requirement imposed by the US-FDA, Provepharm is required to conduct a clinical study to evaluate the safety and efficacy of ProvayBlueTM for the treatment of acquired methemoglobinemia. The minimal efficacy endpoints should include achieving a 50% reduction in metHb within 1 hour of the first dose of ProvayBlueTM in addition to normalization of the respiratory rate, heart rate and blood pressure within 2 hours of the first dose of ProvayBlueTM (refer to Section 6.1).

This is a prospective, interventional, open label, uncontrolled Phase 4 study to confirm that ProvayBlueTM is efficacious and safe in patients with acquired methemoglobinemia.

The open-label conduct of the trial allows for rapid assessment of the drug-relatedness status of any toxicity.

8.3. TRIAL TIMETABLE (STUDY PERIODS)

The trial includes the following visits:

- Screening and enrolment
- Study Treatment
 - H0: ProvayBlueTM Dose 1
 - H1: 1 hour after the end of ProvayBlueTM infusion. Administration of ProvayBlueTM Dose 2 (if applicable)
 - H2: 2 hours after the end of ProvayBlue™ Dose 1 infusion
 - H3: 2 hours after the end of ProvayBlueTM Dose 2 infusion (if applicable)
- H24 (24 hours after the end of ProvayBlueTM Dose 1 infusion)
- Hospital Discharge (if earlier than H24)
- Follow up visit (5 -10 days following the last ProvayBlueTM administration)
- Follow up call (10 -15 days following the last ProvayBlueTM administration)

9. SELECTION AND WITHDRAWAL OF PATIENTS

10 patients (adults and pediatric population of all ages) diagnosed with acquired methemoglobinemia and treated with ProvayBlueTM will be included in the study.

9.1. INFORMED CONSENT

Each potentially eligible patient (and their parent[s] or legally authorized representative[s] as applicable) will be informed of the study's objectives and overall requirements.

ProvayBlueTM will be administered as per the treating physician's diagnosis and hospital standard of care. It may be possible that the patient will be administered their first dose of ProvayBlueTM as per standard of care prior to obtaining the consent for this study. However, patient consent (and their parent[s] or legally authorized representative[s] as applicable) MUST be obtained prior to any data collection (retrospective and prospective) for this study and study specific assessments.

The Investigator will explain the study fully to the patient (as relevant) and his/her parent(s)/legally authorized representative(s) (as required) using the PICD approved by the institution's Independent Ethics Committee (IEC)/ Institutional Review Board (IRB). If a parent/legally authorized representative is willing for the patient to participate in the study, (s)he will be requested to give written informed consent. The PICD will be signed and personally dated by **both** a parent/legally authorized representative and the Investigator.

If capable, the patient should provide assent/consent to participate in the study and also sign and personally date the Informed Consent if possible (according to local laws and regulations).

A copy of the signed form will be provided to the parent(s)/ legally authorized representative(s) and the original retained with the source documents.

Although nursing staff may be involved in describing the trial to a patient and his/her parent(s)/legally authorized representative(s), the Investigator must participate in discussions with the patient and his/her parent(s)/legally authorized representative(s) and sign and personally date the PICD.

9.2. INCLUSION CRITERIA

To be eligible for inclusion into this study, each patient must fulfil the following inclusion criteria:

- 1. Pediatric or adult patients (males and females of all ages are included) diagnosed with acquired methemoglobinemia and receiving treatment with ProvayBlueTM as per the treating physician's diagnosis and hospital standard of care.
 - Acquired methemoglobinemia is defined as a level of methemoglobinemia >30% or $\le 30\%$ with associated clinical symptoms (e.g. sleepiness, cyanosis, dizziness, etc.).
- 2. Written informed consent obtained prior to any data collection (retrospective and prospective) for this study and study specific assessments.

9.3. EXCLUSION CRITERIA

To be eligible for inclusion into this study, each patient must violate none of the following exclusion criteria:

- 1. Known severe hypersensitivity reactions to methylene blue or any other thiazine dye.
- 2. Known deficiency in glucose-6-phosphate dehydrogenase (G6PD) due to the risk of hemolytic anemia as well as lack of therapeutic effect.
- 3. Known deficiency in NADPH reductase.
- 4. Known use of selective serotonin reuptake inhibitors (SSRIs), serotonin and norepinephrine reuptake inhibitors (SNRIs), MonoAmine Oxidase (MAO) inhibitors or drugs metabolised via CYP isoenzymes anticipated during the treatment phase of the study (see Section 11.2).
- 5. Women who refuse to stop breastfeeding for up to 8 days after receiving the last dose of ProvayBlueTM (see Section 11.2).

9.4. ASSIGNMENT OF PATIENT NUMBER

All patients who sign the PICD will be allocated a patient number sequentially at each center. The number of any patient who is withdrawn from the study will not be reallocated.

9.5. PREMATURE WITHDRAWAL OF PATIENTS FROM STUDY AND REPLACEMENT POLICY

9.5.1. Discontinuation Criteria

Patients (and their parent[s] or legally authorized representative[s] as applicable) will be informed that they have the right to withdraw from the study at any time, without prejudice to their medical care, and are not obliged to state their reasons. Any withdrawals must be fully documented in the CRF and should be followed up by the Investigator.

Additionally, the Investigator may withdraw a patient from the study or from ProvayBlueTM administration at any time if he/she considers this to be in the patient's best interest.

Patients MUST be discontinued from the study for any of the following reasons:

- Severe or life-threatening hypersensitivity/allergic reaction (refer also to Section 11.4.1);
- Hemolytic anemia (refer also to Section 11.4.2);
- Changes in medical status of the patient such that the Investigator believes that patient safety will be compromised;
- Death:
- Withdrawal by patient or at the request of their legally authorized representative;
- Physician decision;
- At the specific request of the Sponsor;
- Study terminated by Sponsor.

Patients MAY be discontinued from the study for any of the following reasons:

- Adverse events including serious intercurrent illness or significant worsening of intercurrent illness;
- Protocol violations, including non-compliance with study assessment and patient refusal;
- Other study-specific reasons;
- If a patient fails to return for a scheduled visit/follow-up, 3 attempts should be made to contact the patient to ensure that the reason for not returning is not an AE. Likewise if a patient declares his/her wish to discontinue from the study, e.g. for personal reasons.

If the ProvayBlue™ therapy is prematurely discontinued, the primary reason for discontinuation must be recorded in the appropriate section of the CRF and all efforts will be made to complete and report the observations as thoroughly as possible. Discontinuing of ProvayBlue™ administration is not a reason to discontinue from the study. Every effort should be made to collect complete information on patients whether ot not they complete the planned treatment.

A complete final evaluation following withdrawal from the study should be made, as described in Section 12.5, and any AEs will be followed 10 to 15 days from the last dose of ProvayBlueTM.

The study will be terminated if, in the opinion of the Investigator and the Sponsor, significant safety concerns arise during the conduct of the study.

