6.6. RISK-BENEFIT ASSESSMENT

ProvayBlueTM will be administered to the study patients to treat acquired methemoglobinemia resulting in a direct health benefit.

Refer to APPENDIX 1: US Package Insert of ProvayBlueTM for the risks associated with the use of ProvayBlueTM.

Entering a patient who requires methylene blue treatment, especially minors, into the protocol is associated with minimal incremental risk to the patient. The treating physician/Investigator and other treating health care professionals should continuously monitor the patient to ensure that the degree of burden and risk to the patient is minimized.

Extreme caution should be exercised when administering to newborns and infants below the age of 3 months due to lower concentrations of NADPH-methemoglobin reductase necessary for reducing methemoglobin to hemoglobin, making these infants more susceptible to methemoglobinemia produced by high doses of methylthioninium chloride.

The approximate volume of blood planned for collection from each patient over the course of the study presents no undue risk to the patients, nor does the collection of additional blood in the event an indwelling cannula is utilized (for wasting to ensure clean sample) or for recheck of safety labs, if deemed necessary by the Investigator.

As per regulations and guidelines, a limited volume of blood will be drawn from each patient during this study. Blood drawn from pediatric patients will not exceed the recommended maximum blood sampling volume for children in clinical trials which should not exceed 1% of total blood volume in one draw and 3% of total blood volume within a 4-week period (European Medicines Agency [EMA] guideline). Refer to APPENDIX 3: estimates of 1% of the patient's blood volume for the maximum volume of blood that can be drawn per patient. The number of attempts of venous punctures in children and adolescents will be restricted to a maximum of 3 attempts.

The safety data collected by this protocol (i.e., physical examination, vital signs, laboratory analysis [including metHb], and adverse event [AE]) are adequate to protect the patient's safety and should detect all expected treatment-emergent AEs (TEAEs).

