11.4.1. Hypersensitivity

Anaphylactic reactions to methylene blue class products have been reported. Patients treated with ProvayBlueTM should be monitored for anaphylaxis. If severe or life threatening allergic reaction (e.g., angioedema, urticaria, bronchospasm) should occur, discontinue ProvayBlueTM and initiate supportive treatment. Refer also to APPENDIX 1: US Package Insert of ProvayBlueTM for further information.

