11.4.2. Hemolytic Anemia

Hemolysis can occur during treatment of methemoglobinemia with ProvayBlueTM. Laboratory testing may show Heinz bodies, elevated indirect bilirubin and low haptoglobin, but the Coombs test is negative. The onset of anemia may be delayed 1 or more days after treatment with ProvayBlueTM. In the event that a patient has hemolytic anemia, discontinue ProvayBlueTM and initiate appropriate treatment (e.g. red blood cell transfusion). Refer also to APPENDIX 1: US Package Insert of ProvayBlueTM for further information.

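### Protocol 9.5.1 takes a patient out of the study, not only off ProvayBlue, after severe hypersensitivity, so no blood count is guaranteed at or after 24 h, when delayed hemolysis could appear

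*Protocol*

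**What the plan says.** Protocol 9.5.1 opens its mandatory list with "Patients MUST be discontinued from the study for any of the following reasons". The first bullet is "Severe or life-threatening hypersensitivity/allergic reaction (refer also to Section 11.4.1"; the second is hemolytic anemia.

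The cross-referenced sections ask for less. Section 11.4.1 says that if such a reaction "should occur, discontinue ProvayBlueTM and initiate supportive treatment". Section 11.4.2 reads "In the event that a patient has hemolytic anemia, discontinue ProvayBlueTM and initiate appropriate treatment". Neither mentions leaving the study. Further down, 9.5.1 says that ending ProvayBlue administration does not in itself justify ending study participation.

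For patients who leave, 9.5.1 provides the following:

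- "A complete final evaluation following withdrawal from the study should be made, as described in Section 12.5", with AEs followed to 10-15 days after the last dose.
- Withdrawals are to be documented and followed up by the Investigator.
- If therapy is stopped early, "all efforts will be made to complete and report the observations as thoroughly as possible". Also, "Every effort should be made to collect complete information on patients", whether or not planned treatment is completed.

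Section 12.5 lists symptoms, vital signs, biochemistry, hematology, metHb, concomitant therapy and AEs. It gives no day or window and includes neither ECG nor physical examination.

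Patients still in the study have hematology and biochemistry within 1 h of the end of infusion, at about 24 h or at discharge if sooner (12.2), and at the Day 5-10 visit (12.4).

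**The concern.** Stopping the drug protects a patient who has reacted to it. Ending the visit schedule adds no protection and removes the timed safety samples. The bullet therefore conflicts with the section it cites and with the retention principle in 9.5.1.

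The samples matter because 11.4.2 treats hemolytic anemia as an expected event that can begin a day or more after dosing. Section 6.6 says that the safety data, laboratory analysis included, "should detect all expected treatment-emergent AEs". For a patient withdrawn early for hypersensitivity, the protocol does not secure a blood count late enough to support that statement.

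**Working it through.** The plan gives no figure on this point, so the check sets the required blood counts beside the stated onset of delayed hemolysis.

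**Inputs**
- Onset of anemia: can be 1 day or more after treatment (11.4.2).
- Infusion: 5-30 minutes (8.1). Withdrawal for a hypersensitivity reaction can therefore fall on the day of dosing. The documents do not fix the time, so this is an assumption.
- Section 12.5 sample: one, untimed. Its timing is a second, separate assumption.

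**Step 1. All required post-dose counts, single dose, on schedule.** Within 1 h + 24 h/discharge + Day 5-10 = 3. The flow chart also marks hour 2 for hematology and biochemistry, which would make 4; Section 12.2 lists no such sample for a patient without Dose 2. The extra mark does not affect the next step.

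**Step 2. Required counts at or after 24 h, with withdrawal on the day of dosing and the reaction resolved**

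| | Inpatient at 24 h | Discharged before 24 h |
|---|---|---|
| Kept on schedule | 1 (24 h) + 1 (Day 5-10) = 2 | 1 (Day 5-10) |
| Withdrawn, 12.5 sample the same day | 0 | 0 |
| Withdrawn, 12.5 sample at 24 h or later | 1 | 1 |
| Shortfall, same-day sample | 2 - 0 = 2 | 1 - 0 = 1 |
| Shortfall, later sample | 2 - 1 = 1 | 1 - 1 = 0 |

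The zero depends on a same-day 12.5 sample. If withdrawal comes only after the 24 h or discharge sample, one scheduled count (Day 5-10) is replaced by one untimed count.

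**Step 3. What remains after withdrawal, and whether it supplies a timed count**
- More frequent evaluations (12.5) apply while an AE is ongoing; a resolved reaction does not trigger them.
- Following abnormal laboratory values to baseline or stability (15.3.3.1) presupposes that an abnormal value was found.
- AE follow-up to Day 10-15 names no blood draw. It can pick up anemia with reported symptoms.
- The effort sentences and the instruction to follow up withdrawals name no test or time.
- Package insert 2.1 names vital signs, ECG and metHb for monitoring. Insert 5.4 describes the delayed anemia and its laboratory findings but sets no schedule of counts.

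**Step 4. How likely the trigger is.** The documents give no rate of severe hypersensitivity. For an assumed per-patient rate q, the chance of at least one case among the 7 enrolled (SAP Section 1) is 1 - (1 - q)^7. At q = 1% this is 1 - 0.99^7 = 6.8%; at q = 5% it is 1 - 0.95^7 = 30.2%. This is the chance that the bullet applies to someone. The chance of a missed hemolysis is smaller, because further conditions must hold.

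**The case against.** The strongest reply is that a withdrawn patient does have a required blood count. Section 12.5 includes hematology, and a site may draw it at 24 h or later. This stands. A reader might infer that withdrawal leaves no required count at all, or none in the relevant period. The documents support only that one count is required and that its timing is not secured.

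Second, the sentence on stopping the drug and the instruction that withdrawals be followed up suggest that the authors meant to keep following such patients. This also stands, and makes the point a conflict of wording. It would go too far to read 9.5.1 as a deliberate decision to abandon follow-up. The bullet as written nevertheless mandates leaving the study, and the general instructions do not restore a dated sample.

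Third, harm needs a chain of events: a severe reaction on the day of dosing, prompt resolution, a same-day 12.5 sample, then delayed hemolysis without reported symptoms through Day 10-15. Severe reactions may well be prolonged and so bring repeat evaluations. Known G6PD deficiency and known severe hypersensitivity are excluded (9.3), and insert 5.4 warns the treating clinician. All of this lowers the severity.

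Fourth, the SAP already plans per-patient hematology plots against relative time (6.3.2) and Listing 16.2.11.1, so the timing of any late count will be visible. What remains unplanned is the reason for leaving. The disposition table (SAP 4.1) reports analysis sets and 10-day status, and a withdrawal that follows the protocol would not appear as a deviation (SAP 4.4).

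**Conclusion.** The point holds, at low severity. The hypersensitivity bullet in 9.5.1 conflicts with 11.4.1 and with another sentence of 9.5.1. Assuming withdrawal on the day of dosing, resolution of the reaction and a same-day 12.5 sample, required counts at or after 24 h fall from 2 (or 1 after early discharge) to 0. The exposure is limited to hemolysis without reported symptoms.

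The primary endpoint is little affected: it is read within 1 h of the first dose, and the 12.5 evaluation includes metHb.

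Two further inferences are not supported. One is that patients with hemolysis go unfollowed under the second bullet: once recognized, hemolysis is an ongoing AE with repeat evaluations (12.5) and laboratory follow-up (15.3.3.1), so little is lost there. The other is that this study missed a case: the documents do not say whether any of the 7 enrolled patients left under this bullet.

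**What to change.** In 9.5.1, change the hypersensitivity bullet to mandatory discontinuation of ProvayBlue. The hemolysis bullet may be aligned for consistency, with little practical effect. Add one sentence: dosed patients who have not withdrawn consent stay on the existing schedule, at least through the Day 5-10 hematology and biochemistry sample and the Day 10-15 call. The cost is one or two bullets and a sentence, using visits already planned.

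Enrollment closed on 31 August 2020 (SAP Section 1), so rewording cannot change follow-up already done. For this study, the narratives planned in SAP Section 4 should state whether any patient left under this bullet and, if so, when the last blood count was taken. That is one sentence per affected patient, or one sentence saying there were none; no new table is needed.

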9.5.2. Replacement Policy

Should a patient drop out or be withdrawn from the study, his/her patient number will not be reallocated. During the study, recruitment may be increased in order to include 10 evaluable patients. A patient will be considered evaluable if he/she is diagnosed with acquired methemoglobinemia (refer to Section 6.3), received a first dose of ProvayBlueTM of 1 mg/kg and had adequate available data to measure the primary efficacy analysis.

10. STUDY MEDICATION

Patients will receive treatment with ProvayBlueTM as per the treating physician's diagnosis and hospital standard of care.

ProvayBlueTM has been approved by the US FDA for patients to be administered IV at a dose of 1 mg/kg over 5-30 minutes and if the metHb level remains above 30% or if clinical symptoms persist, to give a repeat dose of up to 1 mg/kg 1 hour after the first dose.

Depending on the clinical status of the patient, additional doses may be administered at the discretion of the Investigator. The data on these additional doses will be recorded in the study CRF. If ProvayBlueTM is administered as an infusion, it MUST be diluted in 5% dextrose in water (D5W) only. Dilution in saline will result in precipitation of the product and must not be administered.

For further information regarding ProvayBlueTM, including packaging, labelling, presentation, storage and preparation prior to patient administration, please refer to the prescribing information for ProvayBlueTM in APPENDIX 1: US Package Insert of ProvayBlueTM.

11. CONCOMITANT THERAPY/MEDICAL MANAGEMENT OF ADVERSE EVENTS (AEs)

Medications or clinical interventions, which are considered necessary for the patient welfare or to assist in the management of AEs, may be given at the discretion of the Investigator.

Refer to APPENDIX 1: US Package Insert of ProvayBlueTM for further information on potential drug interactions with ProvayBlueTM.

Safety measures are to be considered for certain concomitant medications. These medications are included in Section 11.2. Medications that are prohibited during the course of this study are listed in Section 11.3.

11.1. RECORDING OF PREVIOUS CONCOMITANT THERAPY

All concomitant therapy received during the study, from PICD signature or the start of ProvayBlueTM treatment (whichever occurs sooner) until the follow up visit, will be recorded using the generic terms. The use of herbal/natural products, as well as diagnostic, therapeutic or surgical procedures performed during the study period will be recorded as concomitant therapy.

All prescription, non-prescription, or over-the-counter medications including herbal remedies given to or taken by the patient before inclusion in the study at study entry and within 4 weeks prior to study entry, must be clearly documented on the prior medications CRF.

Investigational ProvayBlueTM should be used for this study/ However, commercial ProvayBlueTM that could be administered for treatment of acquired methemoglobinemia prior to study entry as per hospital standard of care must be retained at the site until the monitoring visit of the Orion Clinical Research Associate (CRA) and all information need to be recorded in the CRF. In particular, batch number, expiration date and reason for not using investigational product should be captured on the drug accountability log.

11.2. PRECAUTIONS FOR USE, INTERACTIONS WITH OTHER MEDICINAL PRODUCTS AND OTHER FORMS OF INTERACTION OF THE IMP

Agents Metabolized by Cytochrome P450 Enzymes

Methylene blue inhibits a range of Cytochrome (CYP) isozymes *in vitro*, including 1A2, 2B6, 2C8, 2C9, 2C19, 2D6 and 3A4/5. This interaction could be more pronounced with narrow therapeutic index drugs that are metabolized by one of these enzymes (e.g., digoxin, warfarin, phenytoin, alfentanil, cyclosporine, dihydroergotamine, ergotamine, fentanyl, pimozide, quinidine, sirolimus and tacrolimus). However, the clinical relevance of these *in vitro* interactions is unknown.

Interaction with other medicinal products and other forms of interaction

Methylthioninium chloride is a potent inhibitor of the transporters OCT2, MATE1 and MATE2-K. The clinical consequences of the inhibition are not known. The administration of methylthioninium chloride Proveblue has the potential to transiently increase the exposure of drugs

primarily cleared by renal transport involving the OCT2/MATE pathway, including cimetidine, metformin and acyclovir.

Methylthioninium chloride is a substrate of P-glycoprotein (P-gp). The clinical consequences are considered likely to be minimal due to the transient and single dose use that normally occurs in the emergency setting.

Contraindications

In Europe patients with chlorate poisoning, nitrite-induced methemoglobinemia during treatment of cyanide poisoning and patients with a deficiency in NADPH (nicotinamide adenine dinucleotide phosphate) reductase are contraindicated for receiving ProvayBlueTM treatment for methemoglobinemia. Although this is not the case in the United States and other countries, special care should be given to ensure the efficacy benefit of administering ProvayBlueTM in patients known to meet these restrictions.

Pregnancy

There are no adequate data from the use of ProvayBlueTM in pregnant women. Studies in animals have shown reproductive toxicity (see section 5.3). The potential risk for humans is unknown. ProvayBlueTM should not be used during pregnancy unless clearly necessary, e.g. in lifethreatening methemoglobinemia.

Breastfeeding

It is unknown whether ProvayBlueTM is excreted in human breast milk. The excretion of ProvayBlueTM in milk has not been studied in animals. A risk to the suckling child cannot be excluded. Based on kinetic data, breastfeeding should be discontinued upon receiving ProvayBlueTM and for a period of 8 days after the administration of the last dose of ProvayBlueTM. Otherwise, breastfeeding patients must be excluded for safety reasons (see also Section 9.3). In case a breastfeeding woman needs specific therapy that is urgently indicated, drugs shall be administered as current standard therapy.

Fertility

In vitro, ProvayBlueTM has been shown to reduce motility of human sperm in a dose dependent manner.

Contraception

Both patients and their partners with child-bearing potential must employ a reliable method of contraception, for example,

- Oral Contraceptive + Condom with Spermicide;
- Inter Uterine Device (IUD) + Condom with Spermicide;
- Diaphragm with Spermicide + Condom with Spermicide;
- Injectable progesterone + Condom with Spermicide;
- Subdermal Implant + Condom with Spermicide;
- Sexual abstinence.

